12.2 Demographic and Baseline Characteristics

The following demographic and baseline data will be summarized in a table by cohort for the EAS.

- Age at informed consent (in years).
- Sex at Birth: Female; Male.
- **Gender Identification**: Female; Male; Transgender Man; Transgender woman; Gender non-conforming; None of the above; Prefer not to answer; Other.
- **Race**: American Indian or Alaska Native; Asian; Black or African American; Native Hawaiian or Other Pacific Islander; White; Other.
- Ethnicity: Hispanic or Latino; Not Hispanic or Latino; Other; Unknown.
- **Childbearing Potential**: Yes; No (the percentage of childbearing potential is based on the number of Females at birth).
- Weight (kg)
- Height (m)
- **BMI** (kg/m²)

The demography and baseline data captured in the CRF will be included in a listing for EAS only.

12.2.1 Medical History

General medical history will be presented in the table by cohort for **EAS**, and the psychiatric medical history will be analyzed in the same manner. The number and percentage of subjects with each medical history term will be summarized by the Medical Dictionary for Regulatory Activities (MedDRA) system organ class (SOC) and preferred term (PT). Medical history will be coded using MedDRA version 26.0 to assign a SOC and PT to each event.

Separate listings for general medical history and psychiatric medical history will be included for **EAS**.

12.2.2 Prior and Concomitant Medications

Medications received prior or concomitantly with study drug (preferred base name), categorized by Anatomical Therapeutic Chemical (ATC) medication subgroup (ATC level 4) or subgroup (ATC level 3, 2 or 1, if level 4 is not available) according to WHODRUG (Version Global B3 MARCH 2023), will be summarized separately in tables for **EAS**. The number and percentage of subjects using each medication will be displayed together with the number and percentage of subjects using at least one medication within each medication group and subgroup.

Prior and concomitant medications will be included together but with "Concomitant Flag" in a listing for EAS.

CCI

Strictly Confidential. © 2023, PRA Health Sciences. All rights reserved.

12.3 Device Application

12.3.1 Directly Observed Ingestion

The following directly observed ingestion (DOI) data for Cohort 1 will be summarized in Table together with positive detection (Section 12.5.1) and latency data (Section 12.5.2) for the FAS-Cohort 1.

• Number of ingestions (15 times; 14 times; 13 times; 12 times; 11 times; 10 times; 9 times; 8 times; 7 times; 6 times; 5 times; 4 times; 3 times; 2 times; Once)

Furthermore, the above information will be provided in a listing based on **FAS-Cohort 1** together with

- The reason if subject does not ingest the miniature IEM tablets
- Date of ingestion
- Time of each ingestion,
- Volume of water (mL) ingested with placebo,
- Detection data
 - Patch serial number
 - Detected (True/False)
 - Patch impedance good (True/False)
 - Valid session (True/False)
 - Invalid session description
 - False positive (True/False)
- Latency data
 - Patch serial number
 - Date and time of detected
 - Date and time displayed
 - Patch detection latency (seconds)
 - Ingestion data transfer latency (seconds)
 - Total detection latency (seconds)
- Did the subject complete all the ingestions
- Was the subject discontinued from completing all ingestions and the reason for discontinuation

12.3.2 Drug Exposure

Drug Exposure is not applicable for Cohort 1 because of placebo tablets.

Page 15 of 20

Strictly Confidential. © 2023, PRA Health Sciences. All rights reserved.

For Cohort 2, subjects will ingest Abilify MyCite at the same dose as their currently prescribed aripiprazole. The following drug exposure data for Cohort 2 will be summarized in a table together with latency data for the **FAS-Cohort 2**.

• The number and percentage of Abilify Dose ingested (2 mg; 5 mg; 10 mg; 15 mg; 20 mg and 30 mg).

Furthermore, above information will be provided in a listing based on FAS-Cohort 2, together with

- Date of Abilify MyCite ingestion
- Time of Abilify MyCite ingestion
- Latency data
 - Patch serial number
 - Date and time of detected
 - Date and time displayed
 - Patch detection latency in seconds
 - Ingestion data transfer latency in seconds
 - Total detection latency in seconds
- The reason if subject does not ingest the current prescribed dose of Abilify MyCite
- Volume of water (mL) ingested with Abilify MyCite

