9.2.3 Full Analysis Set

The **Full Analysis Set (FAS)** comprises all the detections of the wearable sensors done on the subjects who took at least 1 dose of MITs (Cohort 1) or Abilify MyCite (Cohort 2), excluding those detections with device malfunction (invalid session and impedance is bad).

For the primary endpoint in Cohort 1, the **FAS-Cohort 1** is a subset of the FAS and consists all the detections for subjects who took at least 1 dose of MITs (Cohort 1).

For the primary endpoint in Cohort 2, the **FAS-Cohort 2** is a subset of the FAS and consists all the detections for subjects who took at least 1 dose of Abilify MyCite (Cohort 2).

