9.2.4 Safety Analysis Set

The **Safety Analysis Set (SAF)** will consist of all subjects who wear any patch or take any tablet from the trial and have any safety assessment.

| Analyses | SCR | EAS | FAS-Cohort 1 | FAS-Cohort 2 | SAF |
|--|--------------|--------------|--------------|--------------|--------------|
| Subject disposition | | \checkmark | | | |
| Demographic and baseline characteristics | | \checkmark | | | |
| Medical history | | \checkmark | | | |
| Prior and concomitant medications | | \checkmark | | | |
| Directly Observed Ingestion | | | \checkmark | \checkmark | |
| Study Drug Exposure | | | | \checkmark | |
| Patch Application and Removal | | | \checkmark | \checkmark | |
| Protocol deviation | | \checkmark | | | |
| Positive Detection Accuracy | | | \checkmark | | |
| Detection Latency Measures | | | \checkmark | \checkmark | |
| Adverse Events | \checkmark | | | | |
| Treatment-Emergent Adverse Events (TEAEs) | | | | | \checkmark |
| Deaths and Serious TEAEs | | | | | \checkmark |
| Vital Signs | | | | | \checkmark |

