12.3.3 Patch Application and Removal

As defined in **Table 1**, a minimum of three patch placement photos are required and recorded in the CRF: prior to initial dose, after completion of DOI(s), and when the subject returns for follow-up (prior to patch removal). The following data will be provided in listings for **FAS**:

- Photographs taken prior to initial dose (Yes or No; the reason if no; date and time of photography)
- Patch Application completed (Yes or No; the reason if no; date and time of completion)
- Photographs taken after DOIs (Yes or No; the reason if no; date and time of photography)
- Was the subject instructed to keep the patch on as long as possible? (Yes or No)
- Was subject instructed to return patch to the trial site during follow-up visit? (Yes or No)
- Photographs taken prior to patch removal (Yes or No; the reason if no; date and time of photography)
- Patch Removal completed (Yes or No; the reason if no; date of completion; Patch removal/fell off date and approximate time if it is not on the same date as the visit)
- Patch returned (Yes or No; the reason if no)

CCI

Strictly Confidential. © 2023, PRA Health Sciences. All rights reserved.

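### Abilify MyCite exposure and observed ingestions are reported on detection-based sets that exclude device-malfunction records, so a swallowed dose can drop out of those outputs

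*SAP*

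**What the plan says.** SAP 9.2.3 defines the Full Analysis Set (FAS) in terms of patch records. It "comprises all the detections of the wearable sensors done on the subjects who took at least 1 dose of MITs (Cohort 1". Subjects in Cohort 2 who took Abilify MyCite are covered in the same way. Malfunction records are then left out by this clause: "excluding those detections with device malfunction (invalid session and impedance is bad". FAS-Cohort 1 and FAS-Cohort 2 are each defined as subsets of this set. SAP 10.6 counts the PDA denominator within FAS-Cohort 1 and notes that malfunction sessions are already out of that set.

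The following outputs use these sets:

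- **Cohort 2 exposure table (SAP 12.3.2):** "The following drug exposure data for Cohort 2 will be summarized in a table together with latency data for the" FAS-Cohort 2.
- **Cohort 2 exposure listing (SAP 12.3.2):** "above information will be provided in a listing based on FAS-Cohort 2, together with" ingestion date and time, latency data and related items.
- **Cohort 1 number-of-ingestions table (SAP 12.3.1):** shown "together with positive detection (Section 12.5.1) and latency data (Section 12.5.2) for the FAS-Cohort 1". The accompanying listing is also on FAS-Cohort 1. It carries a patch-impedance flag, a valid-session flag and an entry called "Invalid session description".
- **Patch application and removal (SAP 12.3.3):** "The following data will be provided in listings for" FAS.

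The analysis-set grid in SAP 9.2.5 agrees. TEAEs are reported on the Safety Analysis Set (SAF), which is "all subjects who wear any patch or take any tablet from the trial and have any safety assessment".

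**The concern.** Exposure and ingestion counts describe what subjects swallowed. Protocol section 8 (Testing Visit) has staff give each tablet, watch it being taken, check the mouth and record the time on the eCRF. Protocol 8.10.1 takes the number of ingestions from the eCRF and only the positive detections from the mobile device. A set filtered on patch function is therefore the wrong base for exposure.

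The protocol's own set had no such filter. Its ITT population (protocol 9.2) is made up of subjects who took at least 1 dose. SAP 6.1 records the move from ITT to FAS as a minor difference and does not mention the malfunction exclusion.

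Three things are at stake. The Cohort 2 exposure table may not match the TEAE denominator. The Cohort 1 ingestion table may understate the tablets taken. The session-validity fields in the Cohort 1 listing may be unable to show the failures they were included to document. Poor impedance is a foreseen event: the protocol's Testing Visit text discusses it as a cause of missing tablet registration and allows extra enrolment to make up missing ingestions. A Cohort 2 subject whose session failed could thus have swallowed aripiprazole and still be absent from the exposure output.

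**Working it through.** **Planned totals (protocol 9.1, SAP 8.1).** Cohort 1: 24 subjects × 15 ingestions = 360, as stated. Cohort 2: 30 subjects × 1 ingestion = 30, as stated.

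**Tracing the sets.**

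1. The FAS is built from detections, less malfunction records (SAP 9.2.3).
2. Both cohort sets are subsets of the FAS, so both inherit the exclusion. SAP 10.6 confirms this for FAS-Cohort 1. For FAS-Cohort 2 it follows from the subset wording alone.
3. The exposure and ingestion outputs use those two sets (SAP 9.2.5, 12.3.1, 12.3.2). None is assigned to the SAF or to a subject-based treated set.
4. A Cohort 2 subject has one ingestion. If that session is excluded, no record remains in FAS-Cohort 2, and the dose leaves both table and listing. The subject still meets the SAF definition if any safety assessment was made.
5. A Cohort 1 subject has up to 15 ingestions. An excluded session removes one record, and the subject stays in the set while any other record remains.

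**Size in Cohort 2.** The documents give no malfunction rate, so the number of excluded sessions, m, is an assumption.

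- Share of doses omitted = m / 30. For m = 1, 1/30 = 3.3%; for m = 3, 3/30 = 10%.
- Subjects left in the exposure table = 30 − m, that is 29 to 27. The TEAE denominator would stay at 30.
- Each subject's weight in the dose percentages = 1/(30 − m). At m = 3 this is 1/27 = 3.7% in place of 3.3%.

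**The same over an assumed exclusion rate p per session, with sessions independent.**

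| p | Cohort 2 doses missing, 30p | Chance at least one is missing, 1 − (1 − p)^30 | Cohort 1 records missing, 360p | Cohort 1 completers with fewer than 15 records, 24 × [1 − (1 − p)^15] |
|---|---|---|---|---|
| 1% | 0.3 | 26% | 3.6 | 3.4 |
| 2% | 0.6 | 45% | 7.2 | 6.3 |
| 5% | 1.5 | 79% | 18 | 12.9 |
| 10% | 3.0 | 96% | 36 | 19.1 |

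The last column becomes a misstated ingestion count only if counts are taken from the records left in the set. Independence is also doubtful in Cohort 1: failures would tend to cluster within a subject, which would spread the same number of lost records over fewer subjects.

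**The Cohort 1 listing against its set.** If either an invalid session or bad impedance is enough for exclusion, the listing cannot contain a failure on either flag. If both are required, it can show sessions failing on one flag but still omits those failing on both. The Cohort 2 listing has no such fields, so it would carry no trace of an excluded dose.

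**The case against.** The best reply is that the SAP also treats the FAS as a set of subjects. SAP 12.1 counts subjects in the EAS, FAS and SAF. SAP 12.3.3 lists per-subject items such as photographs and patch return on the FAS. The listings in SAP 12.3.1 and 12.3.2 ask why a subject did not take a tablet, which cannot be a property of a detection. On this view, subject-level outputs cover everyone with at least 1 dose, and the exclusion acts only on detection records. The fields describing invalid sessions point the same way. This shows that the SAP is inconsistent; it does not cancel the stated exclusion, which a programmer would have to apply.

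Four stronger readings are tempting, and the documents do not support them:

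- **That bad impedance alone removes a dose.** SAP 9.2.3 joins the two conditions with an and, so both may be required. The wording is ambiguous, and the number of records lost depends on it.
- **That a Cohort 1 subject who swallowed 15 tablets, two of them in malfunction sessions, will be tabulated as 13.** Ingestion counts come from the eCRF (protocol 8.10.1) and could be programmed from there for any subject still in the set. The SAP does not say which source is used.
- **That failed sessions or patches become untraceable.** SAP 12.1 reports EAS, FAS and SAF counts, and reports on the EAS how many subjects completed all ingestions. A gap would be partly visible, although without dose, patch or reason. In the patch listing, a Cohort 1 subject is lost only if every session is excluded; a Cohort 2 subject is lost after one.
- **That the SAF is the natural replacement.** It admits subjects who wore a patch but swallowed nothing and leaves out anyone without a safety assessment, so it is not the set of subjects who took a tablet.

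It is also fair to say that the practical impact may be small: one dose per subject, at the strength already prescribed, in a descriptive table.

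**Conclusion.** The point holds for the exposure and ingestion outputs. Followed as written, SAP 9.2.3 with 9.2.5 and 12.3.2 drops a Cohort 2 subject from the exposure table and listing when that subject's only session is excluded, while the subject remains in the TEAE denominator. For illustration, 1 to 3 excluded sessions would omit 3.3% to 10% of 30 doses; that range is assumed, and the actual number also depends on how the two exclusion conditions combine. In Cohort 1, understated counts are possible but not certain, and the listing's fields conflict with the set on which it is based.

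A reader might infer that the primary or safety results are at risk. They are not affected by this point: PDA and latency are meant to use the FAS sets, and TEAEs use the SAF. The plan should correct the matter before programming, but it is a reporting fault and does not threaten the trial's conclusions.

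**What to change.** In SAP 9.2.5 and 12.3:

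1. Base Drug Exposure and Directly Observed Ingestion, tables and listings, on all subjects who took at least 1 dose (the protocol's ITT definition), by cohort, and state that every ingestion on the eCRF is counted.
2. Base the Patch Application and Removal listing on all subjects who had a patch applied.
3. Keep the impedance, valid-session and invalid-session fields in the Cohort 1 listing and add them to the Cohort 2 listing.
4. Confine FAS-Cohort 1 and FAS-Cohort 2, with the malfunction exclusion, to PDA and latency. State in SAP 9.2.3 whether one condition or both are needed for exclusion.

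The cost is SAP wording and a different population flag in a few tables and listings, plus the added fields in one listing. No new data collection is proposed.

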12.3.3 Patch Application and Removal

As defined in **Table 1**, a minimum of three patch placement photos are required and recorded in the CRF: prior to initial dose, after completion of DOI(s), and when the subject returns for follow-up (prior to patch removal). The following data will be provided in listings for **FAS**:

- Photographs taken prior to initial dose (Yes or No; the reason if no; date and time of photography)
- Patch Application completed (Yes or No; the reason if no; date and time of completion)
- Photographs taken after DOIs (Yes or No; the reason if no; date and time of photography)
- Was the subject instructed to keep the patch on as long as possible? (Yes or No)
- Was subject instructed to return patch to the trial site during follow-up visit? (Yes or No)
- Photographs taken prior to patch removal (Yes or No; the reason if no; date and time of photography)
- Patch Removal completed (Yes or No; the reason if no; date of completion; Patch removal/fell off date and approximate time if it is not on the same date as the visit)
- Patch returned (Yes or No; the reason if no)

CCI

Strictly Confidential. © 2023, PRA Health Sciences. All rights reserved.

12.4 Protocol Deviations

The protocol deviations will be captured in CRF. Per protocol set is not applicable in this study, and no data review meeting is planned prior to database lock to finalize the evaluable subjects set. All protocol deviations will be listed only based on **EAS**.

12.5 Primary Analyses

The primary analyses including Positive Detection Accuracy and Detection Latency Measures are described in the following sections.

12.5.1 Positive Detection Accuracy

For **FAS-Cohort 1**, the number of positive detections, the positive detection accuracy (PDA) and 95% Clopper-Pearson confidence interval (CI) will be summarized, for overall DOIs only.

Positive detections will not be reported in CRF and will rather be downloaded from the trial mobile device(s). All positive detections data will be listed together with directly observed ingestion data (Section 12.3.1) based on FAS-Cohort 1.

12.5.2 Detection Latency Measures

As defined in **Table 3**, the directly observed ingestion time (TSE 1) is recorded in the CRF. Other signal detection times (TSE 2-4) will be downloaded from the trial mobile device(s) for analysis. The derivation of detection latency measures, including Patch Detection Latency, Ingestion Data Transfer Latency, and Total Detection Latency, are provided in **Table 4**.

The three detection latency measures for all DOIs will be summarized using descriptive statistics, for **FAS-Cohort 1** and **FAS-Cohort 2** separately.

Furthermore, two Kaplan-Meier curves will be plotted for all of the latency times (all DOIs), for **FAS-Cohort 1** and **FAS-Cohort 2** separately. The three detection latency measures will be displayed as three curves on the plot. A table will be provided to show the summary of survival status, the median (50% survival time), and 25% and 75% percentiles of survival by Kaplan-Meier estimate.

12.6 Safety Analyses

All safety analyses will be presented for the SAF.

12.6.1 Treatment-Emergent Adverse Events

All AEs reported in the CRF will be coded using MedDRA.

An overall summary of TEAEs, including the number of events reported, and the number and percentage of subjects will be prepared by cohort in a table, as specified below:

- Subjects reporting at least 1 TEAE
- Subjects reporting at least 1 serious TEAE
- Subjects reporting at least 1 device/patch related TEAE
- Subjects reporting at least 1 device/patch related TEAE (by skin irritation score from 0-7)

CCI

Page 17 of 20

Strictly Confidential. © 2023, PRA Health Sciences. All rights reserved.

- Subjects reporting at least 1 clinically significant TEAE (defined by skin irritation score ≥ 2)
- Subjects reporting at least 1 Abilify MyCite treatment related TEAE (Cohort 2 only)
- Subject reported receiving at least 1 TEAE with concomitant or additional therapy
- Subjects with any TEAE leading to death
- Subjects discontinuing the study due to a TEAE
- Subjects discontinuing the study due to a device/patch related TEAE
- Subjects discontinuing the study due to an Abilify MyCite treatment related TEAE

Furthermore, a breakdown of the number and percentage of subjects reporting TEAE, categorized by system organ class (SOC) and preferred term (PT) coded according to the MedDRA dictionary (Version 26.0), will be presented. Note that counting will be by subject not event and subjects are only counted once within each SOC or PT. Therefore, when counting the number of subjects with each event, subjects with multiple events within a particular SOC or PT will be counted under the category of their most severe event within that SOC or PT. The list of TEAE tables is the following:

- TEAEs by SOC and PT
- Clinically significant TEAEs (defined as device/patch related TEAE and skin irritation score ≥ 2) by SOC and PT
- Any TEAE by maximum severity (mild, moderate, severe) by SOC and PT
- Any TEAE related to study device/patch by SOC and PT
- Any TEAE related to Abilify MyCite treatment by SOC and PT (Cohort 2 only)
- Serious TEAEs by SOC and PT
- TEAE leading to death by SOC and PT
- TEAEs leading to study discontinuation by SOC and PT

All AEs recorded on the CRF will be listed with MedDRA SOC and PT. The TEAEs will be marked with a flag within the listing. A footnote will state if no AE occurred after screening and before the subject wore any patches or took any tablet.

Independent listings will be provided with MedDRA SOC and PT for:

- Device/Patch related TEAEs (with skin irritation score evaluation),
- Abilify MyCite treatment related TEAEs (Cohort 2 only),
- TEAEs leading to study discontinuation

12.6.2 Deaths and Serious TEAEs

As already described in previous section, a summary table for TEAE leading to death and for serious TEAEs will be provided by SOC and PT.

Page 18 of 20

Strictly Confidential. © 2023, PRA Health Sciences. All rights reserved.

A listing for all serious TEAEs and for all TEAE leading to death will be prepared.

12.6.3 Laboratory Data

Laboratory data is not applicable in this study.

12.6.4 Vital Signs

Vital sign measurements will be collected at Screening (Visit 1) only, the following vital signs will be summarized in a table:

- Systolic Blood Pressure (mmHg)
- Diastolic Blood Pressure (mmHg)
- Heart Rate (bpm)
- Body Temperature (Fahrenheit)

Vital signs data including abnormal and clinically significant results will be provided in a listing.

